6.2 IMPORTANT PROTOCOL VIOLATIONS

The following table defines the different categories of important protocol violations (PVs). The right-most column describes which PVs will be used to exclude patients from the different patient analysis sets. The final decision about which patients will be excluded from analysis sets will be taken during the course of the study and at report planning meetings before database lock at the latest.

Table 6.2: 1 Important protocol violations

Category/ Code	Description	Example/Comment	Excluded from
A	Entrance criteria not met		
A1.1	No type 2 diabetes		Efficacy / Baseline
A1.2	Patient received Trazenta [®] treatment before registration	This rule will apply for the patients with Trazenta [®]	Efficacy / Safety / Baseline
A1.3	Patient not treated as mono therapy at baseline	1) Used antidiabetic medication but stopped after start of TRZ 2) Used antidiabetic medication and continued after start of TRZ 3) Used antidiabetic medication and changed to non TRZ at start of TRZ 4) No antidiabetic medication until start of TRZ, but start antidiabetic medication with TRZ	Efficacy / Safety / Baseline
A1.4	Registered as other OAD but Trazenta [®]	This rule will apply for the patients with OAD	Baseline
B	Informed consent		
C	Trial medication and randomisation		
C1	Incorrect study medication taken		

Table 6.2: 1(continued) Important protocol violations

Category/ Code	Description	Example/Comment	Excluded from
C1	Incorrect study medication taken		
C1.1	No treatment with Trazenta®	This rule will apply for the patients with Trazenta®	Efficacy / Safety / Baseline
E	Missing data		
E1	No baseline value	No available baseline value of HbA1c for efficacy analysis This rule will apply for the patients with Trazenta®	Efficacy
G	Trial specific		
G	G1	Invalid registration	
G1.1	No patient visit after entry	Patient made no visit after the entry This rule will apply for the patients with Trazenta®	Efficacy / Safety / Baseline
G1.2	Multiple registration	Patient who were already registered this trial with another patient ID In this case, all data for the later patient will not be used.	Efficacy / Safety / Baseline
G1.3	Registration rule not followed		Efficacy / Safety / Baseline
G1.4	Patient started Trazenta® treatment without registration period	This rule will apply for the patients with Trazenta®	Efficacy / Safety / Baseline
G1.5	Not continuous investigation		Efficacy / Safety / Baseline

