## 2. RATIONALE, OBJECTIVES, AND BENEFIT - RISK ASSESSMENT

### 2.1 RATIONALE FOR PERFORMING THE STUDY

In Japan, post-approval execution of post marketing surveillance (PMS) is requested by the Japanese Pharmaceutical Affairs Law (J-PAL) in order to accumulate safety and efficacy data for reexamination. Reexamination period is defined by Japanese Pharmaceutical Affairs Law (J-PAL). New integrant is 8 years for reexamination. Eight years after approval of a new substance, results of PMS need to be submitted as a part of reexamination dossier to the Japanese regulatory authority, the Ministry of Health, Labour and Welfare (MHLW).

Collected data from PMS will be included in the Japanese periodic safety reports and submitted to MHLW on designated dates until the end of reexamination period.

The protocol may be revised because of new information or knowledge obtained in the course of conducting PMS. When a change of the approved label such as in dosage and administration or indications is made during the reexamination period of Trazenta® Tablets (except that for this change a reexamination period is newly designated by MHLW) and NBI finds it necessary to revise this protocol, handling each matter should be discussed and the protocol may be revised. If any issue or concern arises (e.g. suggestion of a potential for clinically significant adverse reaction, remarkable increase in incidence of an adverse reaction, or any issue or concern on safety or efficacy assessment made prior to the approval of Trazenta® Tablets) in the course of PMS, implementation of additional special surveillance or post-marketing clinical trial should be discussed to identify or confirm a cause or estimated cause of such issue. Special surveillance is defined by Japanese Pharmaceutical Affairs Law (J-PAL). It means surveillance for long use or special patient population (elderly, renal/hepatic dysfunction etc.).

The surveillances for long term use in patients with type 2 diabetes mellitus and for type 2 diabetes mellitus patients with renal/hepatic dysfunction as concomitant disease were requested by the PMDA. The rationale of the sample size for surveillance was agreed with the PMDA. To ensure achievement of number of patients entered, NBI will monitor the numbers of patients with type 2 diabetes mellitus and patients with renal or hepatic dysfunction at registration and collection of eCRFs for book 1.

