### 3. DESCRIPTION OF DESIGN AND STUDY POPULATION

#### 3.1 OVERALL DESIGN AND PLAN

Trazenta® Tablets:

This PMS is a prospective study using a continuous investigation system. Patients with type 2 diabetes mellitus **who are treated as monotherapy** are included in the surveillance. No specific criteria (e.g., demographics, baseline characteristics, concomitant drugs in use) are defined for patient enrolment.

Planned number of patients to be entered and have at least one observation after treatment is **1,500**~~3,000~~. Patients with type 2 diabetes mellitus who have never received Trazenta® Tablets (**monotherapy**) will be enrolled in the surveillance. It is exclusively at the physician's discretion whether to initiate linagliptin on patients.

Patients administered Trazenta® Tablets will be registered preferably within 14 days from the day of first administration. Each patient will be observed for 156 weeks (approximately 36 months) after start of the treatment with this product until the end of the PMS or at premature discontinuation and dropout from the PMS. Observations are made at the following time points: before first administration of Trazenta® (baseline) and 12, 26, 40, 52, 64, 78, 104, 130 and 156 weeks after the start of treatment, or at discontinuation.

There are 3 eCRFs for 0-26 (Book 1), 40- 78 (Book 2) and 104-156 weeks (Book 3) individually.

At 26, 78 and 156 weeks after the start of treatment or at discontinuation, data are to be transmitted immediately after entered into eCRF. In case of occurrence of any adverse events, data in corresponding observation period should be immediately entered into eCRF and transmitted.

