#### **4.1.2 Method of assigning patients to treatment groups**

There will be no randomisation, since this is an observational surveillance.

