6.3 PATIENT SETS ANALYSED

The following two analysis sets are defined as in CTP Section 7.3. The safety set will be the basis of all demographic, baseline and safety analyses. Efficacy analysis will be on basis of the efficacy set.

[figure not shown]
- Safety set:
This patient set includes all patients who had no invalid registration, who were dispensed Trazenta® and were documented to have taken at least one dose of Trazenta®. Patients with CRF data which were not ensured by the investigator will be excluded from this patient set.

[figure not shown]
Proprietary confidential information © 2017 Boehringer Ingelheim International GmbH or one or more of its affiliated companies

[figure not shown]
- **Efficacy set:**
This patient set includes all patients with Trazenta[®] in the safety set who have at least one available on-treatment HbA1c value.

Additional analysis set is defined for comparing the baseline date between Trazenta[®] group and other group:

- **Baseline set:**
This patient set includes all patients who had no iPV leading to exclude from baseline set (i.e., category “Baseline”).

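### SAP 6.2 fixes the exclusion codes, but the codes that need judgement are settled while the sponsor already holds adverse event data; a pre-lock deadline alone does not make those decisions independent of outcome

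*SAP*

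**What the plan says.** **The rule.** SAP 6.2 introduces Table 6.2:1 by saying "The right-most column describes which PVs will be used to exclude patients from the different patient analysis sets". The codes and their consequences are therefore set in advance. On timing it says "The final decision about which patients will be excluded from analysis sets will be taken during the course of the study". The same sentence then names an outer limit for these decisions: "at report planning meetings before database lock at the latest".

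**Codes that leave room for judgement.** Each of the four below removes a patient from the Safety, Efficacy and Baseline sets.
- G1.3 reads "Registration rule not followed", with an empty comment cell.
- G1.5, departure from the continuous investigation system, also has an empty comment cell.
- A1.2 covers Trazenta treatment that precedes registration.
- G1.4 refers to a registration period that the table does not define.

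SAP 6.3 adds a Safety-set exclusion outside the table: "Patients with CRF data which were not ensured by the investigator will be excluded from this patient set".

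**What the sponsor sees.** Protocol 4.1.2: "There will be no randomisation, since this is an observational surveillance". Protocol 3.1: "In case of occurrence of any adverse events, data in corresponding observation period should be immediately entered into eCRF and transmitted". Visit data follow at weeks 26, 78 and 156 or at discontinuation. Under protocol 7.3.3 the sponsor assesses causality alongside the investigator, and either assessment alone can make an event an ADR. Protocol 2.1: "Collected data from PMS will be included in the Japanese periodic safety reports". Protocol 7.3 limits the safety and efficacy analyses to the Trazenta group; the comparator group contributes baseline data only.

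**The concern.** A deadline before database lock keeps exclusions honest in a blinded trial because those who decide cannot link a patient to a treatment effect. Here there is no blind. The sponsor has to review adverse events patient by patient in order to classify them, and it does so before the exclusions are final.

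Safety is the primary objective (protocol 7.3.1), and ADR and SAE incidence are its endpoints (protocol 5.2.1). If a loosely defined code is applied with knowledge of whether the patient had an ADR, the incidence can move in either direction, and a reader of the report could not tell. The analyses are descriptive (protocol 7.2), so what is at stake is bias in the reported incidence and mean change, not a type I error rate.

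**Working it through.** **1. Which exclusions need judgement?**

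| Exclusion | What the documents give | Room for judgement |
|---|---|---|
| A1.1, A1.4, C1.1, E1, G1.1, G1.2 | Diagnosis, drug taken, baseline HbA1c present, visit after entry, duplicate registration | Little |
| A1.3 | Four explicit drug-history patterns | Little |
| G1.3 | No criterion. Protocol 3.1 and 3.3 state 14 days as a preference only | Yes |
| G1.5 | Protocol 3.3 describes continuous enrolment by the investigator; the SAP does not say whether a breach removes one patient or all patients of that site | Yes, in its reach |
| A1.2 | Read literally, removes anyone registered after the first dose. Protocol 3.1 accepts such registration, and 3.3 keeps even those registered beyond the 14 days | Yes; the texts must be reconciled |
| G1.4 | Period not defined in the table | Yes |
| CRF data not ensured | No criterion and no code | Yes |

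Protocol 3.3 plans 5-10 patients per site. One ruling under G1.5 could therefore remove a single patient or 5-10 patients, that is 5/1,500 = 0.33% to 10/1,500 = 0.67% of the group.

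**2. Does any planned analysis expose the effect?** SAP 7.8.1 repeats the overall adverse event summary with the A1.3 patients added back. It restores no other code and does not extend to ADRs by SOC and PT or to HbA1c. The visible text plans no table of outcomes in excluded patients.

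**3. The plan's own figure.** Protocol 7.6 aims to see at least one case of an ADR with incidence 0.2% (95% probability) or 0.31% (99%) in 1,500 patients. New and struck-out figures are merged in the text of 7.6; these are the current values. With P = 1 − (1 − p)^n:
- p = 0.002: 1 − 0.998^1500 = 95.04%
- p = 0.0031: 1 − 0.9969^1500 = 99.05%

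The 1,500 reproduces.

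**4. Illustration, rare ADR.** Expected cases: 0.002 × 1,500 = 3, so 3/1,500 = 0.20%. With one affected patient excluded: 2/1,499 = 0.13%. With all three excluded: zero.

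**5. Illustration, overall ADR incidence.** Assume that 2% of patients (30) are excluded, leaving 1,470. The assumed true incidence is 11%, the phase III drug-related rate in protocol 1.2, with a range of 5% to 15%.

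| True rate | Cases | Excluded at random | Excluded patients have twice the rate | All 30 had an ADR | None had an ADR |
|---|---|---|---|---|---|
| 5% | 75 | 5.0% | (75 − 3)/1,470 = 4.9% | 45/1,470 = 3.1% | 75/1,470 = 5.1% |
| 11% | 165 | 11.0% | (165 − 6.6)/1,470 = 10.8% | 135/1,470 = 9.2% | 165/1,470 = 11.2% |
| 15% | 225 | 15.0% | (225 − 9)/1,470 = 14.7% | 195/1,470 = 13.3% | 225/1,470 = 15.3% |

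**6. Illustration, HbA1c.** If a fraction f is excluded and its mean change differs from that of the retained patients by D, the mean shifts by f × D. With f = 0.02 and D assumed at 0.5 to 1.0 percentage points, the shift is 0.01 to 0.02. With an assumed SD of 0.8 to 1.2, the 95% interval half-width is 1.96 × SD/√1,500 = 0.04 to 0.06. The effect on HbA1c is small.

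**The case against.** The strongest reply is that the meeting applies a table written in advance. Most codes are matters of fact, protocol 7.3 already excludes invalid registrations and contracts, protocol 3.3 describes continuous investigation, A1.3 is spelled out, and a deadline exists. All of this stands. A reader might infer that the deadline gives no protection at all; the documents do not support that. The gap is confined to the exclusions marked in step 1.

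A reader might also infer that those who decide know each patient's HbA1c. Sponsor receipt and classification of adverse events is documented. Review of HbA1c by the deciders is only an inference from the eCRF transmission schedule. Protocol 3.1.1, on administrative structure, is in the contents list but its text is not in the available copy, so a separation of duties may be described there.

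The illustrations are constructed. The extremes in step 5 assume that every excluded patient had an ADR, or that none did. Dropping one of three rare cases still leaves the at-least-one-case criterion met, and 0.13% lies well inside the exact 95% interval for 3/1,500 (about 0.04% to 0.58%). The 11% comes from treatment up to 24 weeks that included add-on therapy, whereas this is a 156-week monotherapy study. At twice the average ADR rate, the shift is only 0.2 percentage points.

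Finally, exclusion from an analysis set does not remove a case from adverse event collection (protocol 8.4.1) or from expedited reporting (8.4.2). That limits the consequence for case-level safety oversight. It does not correct the incidence in the study report.

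**Conclusion.** The point holds in a limited form. For G1.3, the reach of G1.5, A1.2, G1.4 and unconfirmed CRF data, a pre-lock deadline does not by itself make exclusion independent of outcome, because the sponsor already holds and classifies the adverse events. The added-back summary in SAP 7.8.1 covers a different code, and only at the overall level.

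The possible effect ranges from negligible (HbA1c, or overall ADR incidence under modest selection) to material for a rare ADR, where one patient in three changes 0.20% to 0.13%. These sizes rest on assumed exclusion fractions and ADR rates; the documents give no exclusion counts. It would be wrong to read the point as saying that exclusions were driven by outcome, since nothing in the documents shows that. Nor is the study simply single-arm: a comparator group exists, with baseline data only. This is a cheap improvement to a primary safety estimate, not a fatal flaw.

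**What to change.** Add to SAP 6.2:

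> Factual codes are assigned by program, including A1.1 from the recorded diagnosis and E1 from whether a baseline HbA1c exists. Cases that need judgement are decided on a listing of registration, contract, dosing, drug-history and visit data that carries no AE, ADR, SAE or follow-up HbA1c data. The dated list of decisions is frozen before outcomes are tabulated for the study report.

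In addition:
- State a measurable criterion for G1.3, the period meant in G1.4, and what counts as CRF data not ensured by the investigator (with its own code). State whether G1.5 removes one patient or all patients of a site.
- Reconcile A1.2 with protocol 3.1 and 3.3.
- In the report, give for each code the number of treated patients removed and how many had an ADR, an SAE or died. This also guards against what the listing cannot prevent, namely that a decider remembers a case.

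Cost: SAP wording, one extra listing and one small table. No new data are needed. The downside is less freedom at the planning meeting.

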**Proprietary confidential information.**

© 2013 Boehringer Ingelheim International GmbH or one or more of its affiliated companies. All rights reserved.

This document may not - in full or in part - be passed on, reproduced, published or otherwise used without prior written permission.

[figure not shown]

Figure 3.1: 1 Overall design of PMS

Other oral antidiabetic drug:

Patients with type 2 diabetes mellitus are included in the surveillance. No specific criteria (e.g., demographics, baseline characteristics, concomitant drugs in use) are defined for patient enrolment.

After the enrolment of each patient for whom Trazenta® Tablets are prescribed, the patient immediately following and initiating any other oral antidiabetic drug should be enrolled.

Planned number of patients to be entered is 1,500~~3,000~~. Patients with type 2 diabetes mellitus starting any other oral antidiabetic monotherapy (naïve or switched from prior therapy of different oral antidiabetic drug) except Trazenta® Tablets will be enrolled in the surveillance.

Patients administered Oral antidiabetic drugs except Trazenta® Tablets will be registered preferably within 14 days from the day of first administration.

After registration data should be entered into eCRF and transmitted using the EDC system.

The baseline data is collected and there is no observation period.

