## 6. INVESTIGATIONAL PLAN

### 6.1 VISIT SCHEDULE

Trazenta® Tablets:

The investigators will enrol patients who are prescribed Trazenta® Tablets. The observation time points will be as follows: before administration of Trazenta® Tablets (baseline), at 12 weeks, 26 weeks, 40 weeks, 52 weeks, 64 weeks, 78 weeks, 104 weeks, 130 weeks and 156 weeks after the start of administration, and at the time of discontinuation of administration.

Other oral antidiabetic drug:

After the enrolment of each patient for whom Trazenta® Tablets are prescribed, the patient immediately following and initiating any other oral antidiabetic drug should be enrolled. Only patient demographic and baseline characteristics will be collected at enrolment. No further assessment is needed.

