### 7.3 PLANNED ANALYSES

The safety and efficacy analyses are applied only on Trazenta® Tablets.

The safety evaluation will be performed on the “safety set” that will include all patients who have received treatment of Trazenta® Tablets except those who are found to have no observation after enrolment, invalid registration, or invalid contract. The efficacy evaluation will be performed on the “efficacy set”, a subset of the safety set, which will include all patients in the “safety set” except those who have no available efficacy data and/or who do not suffer from type 2 diabetes mellitus from the safety set.

Descriptive statistics for the baseline data will be calculated for the patients who are treated with Trazenta® Tablets as well as other oral antidiabetic monotherapy.

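### SAP rule G1.1 drops never-returning patients from the baseline set in the Trazenta group only, so the baseline comparison sets returning Trazenta starters against all other-OAD starters

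*SAP*

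**What the plan says.** SAP Section 6.2 explains its table of important protocol violations as follows: "The right-most column describes which PVs will be used to exclude patients from the different patient analysis sets". In the row for G1.1 (no visit after entry) that column names the efficacy, safety and baseline sets, and the comment limits the rule to one group: "Patient made no visit after the entry This rule will apply for the patients with" Trazenta.

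SAP 6.3 defines the baseline set by the absence of such violations: "This patient set includes all patients who had no iPV leading to exclude from baseline set". Its purpose is also stated: "Additional analysis set is defined for comparing the baseline date between Trazenta" and the other group. SAP 7.1 then computes an ASD for each baseline characteristic and treats a value above 0.1 as meaningful.

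The other-OAD group has no follow-up. Protocol 3.1 says of it: "The baseline data is collected and there is no observation period". Protocol 6.1 says: "Only patient demographic and baseline characteristics will be collected at enrolment. No further assessment is needed".

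Protocol 7.3 lists absence of any observation after enrolment among the reasons for leaving the safety set. Its separate sentence on baseline data carries no follow-up condition: "Descriptive statistics for the baseline data will be calculated for the patients who are treated with Trazenta", and likewise for the other oral monotherapy. SAP Section 4 declares no change from the protocol's methods.

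**The concern.** Protocol 2.2 sets as an objective the baseline characteristics of patients starting Trazenta or another oral monotherapy, and Protocol 2.1 says the aim is to look for differences between drugs. Both populations are defined at the moment treatment starts. Under G1.1 a Trazenta patient must also come back to be counted. A comparator patient need not, and could not be tested on it. An event after baseline thus decides membership of a baseline comparison in one group only.

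Patients who do not return after a first prescription may well differ from the rest, for example in age, inpatient status or disease duration. If they do, removing them from one side shifts that side's means and percentages. The shift could appear as a difference between drugs, or cancel a real one, in a table read against a fixed 0.1 cut-off. A larger sample does not remove it.

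**Working it through.** **No figure in the plan to reproduce.** The documents give no never-return rate and no expected ASD. The only document inputs are the ASD formulas and the 0.1 threshold (SAP 7.1) and 1,500 planned patients per group (Protocol 3.3).

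**Assumptions.**
- f is the fraction of Trazenta patients who never return.
- d is the mean of never-returners minus the mean of returners, in SD of all entered patients.
- Never-returners and returners have equal variance.
- The two entered groups are identical, so the true ASD is 0.

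**Formula (continuous variable).** Setting the entered mean to 0 and the variance to 1, the returners' mean moves by f × d in absolute value, and their variance is w = 1 − f(1 − f)d². The SAP formula then gives

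ASD = f × d / √((1 + w)/2).

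Example, f = 10%, d = 1.0: w = 1 − 0.10 × 0.90 × 1 = 0.91, so ASD = 0.10 / √0.955 = 0.102.

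| f (patients out of 1,500) | d = 0.5 | d = 1.0 | d at which ASD reaches 0.1 |
|---|---|---|---|
| 2% (30) | 0.010 | 0.020 | 4.48 |
| 5% (75) | 0.025 | 0.051 | 1.91 |
| 10% (150) | 0.050 | 0.102 | 0.98 |
| 15% (225) | 0.076 | 0.155 | 0.66 |

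**Binary variable.** Assume 30% prevalence at entry and 50% among never-returners. At f = 10% the prevalence in returners is (0.30 − 0.10 × 0.50)/0.90 = 0.278. The ASD is 0.0222 / √((0.278 × 0.722 + 0.30 × 0.70)/2) = 0.049. At f = 5% it is 0.023.

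**Crossing the flag.** To a close approximation the shift adds to the true difference when both have the same direction and subtracts when they are opposed.
- Shift 0.025, same direction: only a true ASD above 0.100 − 0.025 = 0.075 is carried over the flag. A true 0.06 becomes 0.085 and stays below.
- Shift 0.05, same direction: a true ASD above 0.05 is carried over.
- Shift 0.025, opposite direction: a true ASD between 0.100 and 0.125 drops below the flag.

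**Scale.** The sampling standard error of an ASD near 0 with 1,500 per group is about √(2/1500) = 0.037.

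**Blank fields if these patients are kept.** SAP 7 computes percentages over all patients in the set, with or without a value, unless otherwise specified. Suppose 30% prevalence in both groups and 10% of Trazenta records blank. The Trazenta percentage prints as 0.30 × 0.90 = 27%. If the ASD uses that denominator, it is 0.03 / √((0.27 × 0.73 + 0.30 × 0.70)/2) = 0.066, from blanks alone. Any fix has to deal with this.

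**The case against.** The asymmetry is plain in the text; the case against concerns its importance and its remedy.

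- **The size is assumed.** This stands. At f = 5% and d = 0.5 the shift of 0.025 is below the sampling error of 0.037, and the rule alone reaches 0.1 only if never-returners are many or very different.
- **The Trazenta group is planned as patients with at least one observation, and SAP 6.3 calls the safety set the basis of baseline analyses.** This holds for the safety tables. The observation condition in Protocol 7.6 belongs to the adverse-reaction sample size. The safety set requires Trazenta intake, so it contains no comparator and cannot carry the two-group comparison.
- **The SAP files G1.1 under invalid registration.** Protocol 7.3 lists no observation and invalid registration as separate reasons, and failing to return does not invalidate a registration. Absence of treatment has its own code, C1.1.
- **Final exclusions are decided at meetings before database lock.** True, but the table is the stated basis for those decisions.
- **Keeping these patients may add little.** This largely stands. Under Protocol 6.2.1, registration covers only date of birth, gender, treatment group, start date, indication and serum creatinine, besides identifiers. Other baseline items are separate from registration, Book 1 covers weeks 0 to 26, and nothing shows that it is completed for a patient who never returns. The table does tolerate gaps elsewhere: a missing baseline HbA1c (E1) excludes from efficacy only.

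A reader might extend the criticism to G1.4, which also removes only Trazenta patients. The documents do not support that. G1.4 concerns registration rather than follow-up, its wording is unclear, and G1.3 and G1.5 carry no group restriction and may already cover comparators.

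**Conclusion.** The point holds as a matter of structure: rule G1.1 selects one group on follow-up, in a comparison meant to describe patients at the start of therapy, and Protocol 7.3 does not ask for it.

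The size cannot be found from the documents. Under the assumptions above the artificial ASD is about 0.025 to 0.10 for f of 5% to 10% and d of 0.5 to 1.0. A reader might infer that the rule by itself will produce flagged differences, or that any true ASD somewhat below 0.1 will change sides. Neither follows: most scenarios stay below 0.1 alone, and crossing needs a true ASD within the shift of 0.1 and the right direction. Nor does the point reach the safety or efficacy results, which Protocol 7.3 confines to Trazenta patients. The comparison is descriptive, with no formal inference (Protocol 7.2), so the priority is low to moderate.

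**What to change.** 1. In the SAP 6.2 table, change the G1.1 exclusion to the efficacy and safety sets only. Leave G1.4 as it is.
2. Report the number of Trazenta patients with no visit after entry.
3. In SAP 7.1, show the ASD table with and without these patients, and state that percentages and ASDs use patients with a recorded value, giving that number for each variable.
4. In SAP 6.3, reconcile the sentence that bases baseline analyses on the safety set with the definition of the baseline set.

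The cost is one table cell, a few sentences and one extra table. The benefit is certain only for items held at registration (age, sex, indication, and eGFR where creatinine was entered). For HbA1c, fasting glucose, weight, diabetes duration and prior drugs, it depends on whether baseline fields were entered for patients who never returned. Where they were not, the selection remains, and the counts in items 2 and 3 at least make it visible.
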